### Sample Size Calculation

Based on data from a recent observational study in a similar population [2], we anticipate a fluid balance in the 24 hours up to day 3 (primary outcome) of  $494 \pm 1512$  mL in the usual care group. A sample size of 174 subjects (87 in each group) will have 90% power at a two-tailed significance level of 0.05 to detect a difference in fluid balance of 750 mL over 24 hours. We have allowed for a drop-out rate of 3% and the study will therefore require a total of 180 patients (90 in each group).

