## Outcome measures and analysis

The primary endpoint is the fluid balance (mL) during the 24-hour period up to the beginning of study day 3 [continuous variable, measured using a Student's t-test for independent samples].

Secondary Outcomes		
Feasibility outcomes		
Cumulative fluid balance (mL) from ICU admission until the beginning of study days 3 and day 5, and at ICU discharge	Continuous variables	Independent samples t-test (or non-parametric equivalent)
Rates of recruitment as a proportion of patients screened and as a proportion of all patients admitted to ICU (per site)		Descriptive only
Incidence of significant protocol violations (total number of patients, per site, and by nature of protocol violation)		Descriptive only
Safety outcomes		
Incidence of serious adverse events (SAEs) (number of patients with SAEs as a proportion of total)		Chi-squared test / Fisher's exact test
Incidence of adverse events (AEs) (number of patients with AEs as a proportion of total)		Chi-squared test / Fisher's exact test
Efficacy outcomes		
Change in SOFA scores from baseline to the beginning of day 3 and beginning of day 5, overall and individual organ sub scores	Continuous variable	Multiple regression analysis (with baseline scores as covariate)
Mortality (28-day and 180 day)	Discrete variable	Chi-squared test; Kaplan-Meier survival curves; log-rank test +/- Cox proportional hazards model if assumptions met
Duration of mechanical ventilation in survivors and non-survivors	Continuous variable	Independent samples t-test (or non-parametric equivalent); Kaplan-Meier survival curves; log-rank test; +/- Cox proportional hazards model if assumptions met
Length of ICU stay	Continuous variable	Independent samples t-test (or non-parametric equivalent); Kaplan-Meier survival curves; log-rank test; +/- Cox

		proportional hazards model if assumptions met
Incidence of new acute kidney injury defined as KDIGO Stage 3 (before and after correction for fluid balance) up to the beginning of day 5	Discrete variable	Chi-squared test
Cognitive dysfunction at 180 days	Discrete variable	Chi-squared test
Health-related quality of life (HR-QoL) at 180 days	Ordinal variable	Mann-Whitney test
Incidence of anxiety and depression	Discrete variable	Chi-squared test
Incidence of Post-traumatic stress disorder	Discrete variable	Chi-squared test
Exploratory outcomes		

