Plasma levels of markers of endothelial injury (Angiopoietin I/II and Ang-1/2, Syndecan-1, total protein, plasma albumin, and protein permeability (albumin: $\alpha$ 2-macroglobulin ratio)), absolute levels and change from baseline	Continuous variables	Independent samples t-test (or non-parametric equivalent); Repeated measures ANOVA if applicable. Scatterplots and Pearson's correlation coefficient or non-parametric alternative if applicable.
Plasma levels of Inflammatory mediators e.g. CRP, TNF $\alpha$ , IL6, IL8: absolute levels and change from baseline	Continuous variables	Independent samples t-test (or non-parametric equivalent); Repeated measures ANOVA if applicable. Scatterplots and Pearson's correlation coefficient or non-parametric alternative if applicable.
Cardiac function (echocardiographic measures including left ventricular ejection fraction, E/E' ratio)	Continuous variables	Independent samples t-test (or non-parametric equivalent)
Renal function and injury (plasma and urine levels of Cystatin C and NGAL), absolute levels and change from baseline	Continuous variables	Independent samples t-test (or non-parametric equivalent); Repeated measures ANOVA if applicable. Scatterplots and Pearson's correlation coefficient or non-parametric alternative if applicable.
Cerebral oximetry (NIRS measurement of regional cerebral oxygen saturation), mean and minimum rScO 2 level, proportion of time spent with rScO 2 below thresholds of 50%, 65%, and 75%	Continuous variables	Independent samples t-test (or non-parametric equivalent)
Tissue oxygenation (NIRS measurement of muscle tissue oxygen saturation), mean and minimum rScO 2 level	Continuous variables	Independent samples t-test (or non-parametric equivalent)

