## Secondary analyses

Secondary multiple regression analysis will be performed with treatment allocation as the main exposure. The following key covariates will be forced into the model: age, APACHE II score, presence of ARDS, vasopressor use at baseline. Additional covariates for inclusion in the model will be selected based on clinical plausibility.

We will undertake a secondary per-protocol analysis. This information will be valuable in differentiation between treatment failure (the treatment did not have the intended effect) and process failure (intervention not delivered as intended).

If there is evidence of a difference in the outcome of cognitive dysfunction between treatment groups, we will use path analysis to attempt to ascertain whether the effect of treatment group assignment on cognitive function is mediated by cerebral oxygenation.

For the exploratory outcomes, we will undertake secondary analyses using multivariate regression analysis with fluid balance as the main exposure and treatment group assignment as a covariate.

At a later stage, we will investigate the relationship between cerebral and tissue oxygenation and cardio-respiratory physiological variables such as heart rate, mean arterial pressure, and arterial oxygen saturation.

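### Skewed biomarkers are analysed as raw change from baseline, and in repeated measures and regression models with no log or rank alternative, so proportional effects are harder to detect (minor)

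*SAP*

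**What the plan says.** The exploratory rows of the table in the SAP section Outcome measures and analysis list three groups of markers as continuous variables. Each is to be analysed both as a measured level and as a measured difference from baseline.

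- Inflammatory mediators: "IL6, IL8: absolute levels and change from baseline".
- Renal markers: "Renal function and injury (plasma and urine levels of Cystatin C and NGAL), absolute levels and change from baseline".
- Endothelial markers, which include an albumin to alpha-2-macroglobulin ratio: the row ends "ratio)), absolute levels and change from baseline".

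The methods for all three are "Independent samples t-test (or non-parametric equivalent); Repeated measures ANOVA if applicable", followed by "Scatterplots and Pearson's correlation coefficient or non-parametric alternative if applicable". The table does not say when the non-parametric option replaces the t-test or Pearson's coefficient.

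The section Secondary analyses adds, for the exploratory outcomes, "multivariate regression analysis with fluid balance as the main exposure and treatment group assignment as a covariate". It names no transformation and no baseline value of the marker. The outcome table states baseline as a covariate for the SOFA scores only. No log scale, geometric mean or ratio of means appears anywhere in the SAP.

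**The concern.** Concentrations of cytokines and injury markers, and ratios of such concentrations, are often right-skewed, and treatment effects on them are often closer to proportional than additive. A raw difference then mixes the effect with the patient's starting level. As an illustration, a 30% fall is 30 units from a baseline of 100 and 300 units from a baseline of 1,000. A t-test on such differences is driven by the patients who start high.

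Ranking does not fully solve this. Ranks of a level are the same before and after taking logs, but ranks of a difference are not. The ranked raw change still depends on the size of the baseline.

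The repeated measures ANOVA and the regression on fluid balance have no stated alternative, so a few extreme values can carry weight in both. At stake is the second objective, the exploration of biological effects: a real proportional effect could be missed, and a rank test alone does not give its size.

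**Working it through.** **The plan's own figure first.** The SAP gives a sample size only for the primary outcome: "A sample size of 174 subjects (87 in each group) will have 90% power at a two-tailed significance level of 0.05", for a difference of 750 mL and an SD of 1512 mL.

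- n per arm = 2 × (1.960 + 1.282)² × 1512² / 750² = 85.4, so 86. The SAP has 87, which gives 90.5% power.
- 174 / 0.97 = 179.4, so 180 with 3% drop-out.

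The figure reproduces, and 87 per arm is used below. The SAP makes no power statement for the markers.

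**Assumptions, none of them from the SAP.** Baseline and follow-up values are log-normal with the same log-SD, their correlation on the log scale is 0.5, and the intervention multiplies the follow-up value by 0.70 (a log effect of ln 0.70 = −0.357). Tests are two-sided at 0.05.

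**Arithmetic for the log-scale analyses.** Power ≈ Φ(0.357 / √(2v/87) − 1.96), where v is the variance on the log scale. At log-SD 1.0:

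- log level: v = 1.00, so Φ(2.35 − 1.96) = 65%
- log change: v = 2 × 1.00 × (1 − 0.5) = 1.00, so also 65%
- log follow-up adjusted for log baseline: v = 1 − 0.5² = 0.75, so Φ(2.72 − 1.96) = 78%

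**Simulation at log-SD 1.0.** Ranges are over repeated runs. With 3,000 simulated trials the standard error is at most √(0.25/3000) = 0.9 points.

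| Analysis | Power |
|---|---|
| Level, raw t-test | 45–47% |
| Level, rank test | 60–64% |
| Level, t-test on logs | 65–66% |
| Change, raw t-test | 31–34% |
| Change, rank test on raw change | 49–51% |
| Change, t-test on log change | 63–67% |
| Baseline-adjusted, raw scale | 52–53% |
| Baseline-adjusted, log scale | 75–77% |

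The log-scale rows agree with the arithmetic to within about 3 points.

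**Levels.** The rank test stays close to the t-test on logs: 81% against 83% at log-SD 0.8, 64% against 66% at 1.0, and 43% against 45% at 1.3.

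**Changes.** Across log-SD 0.8 to 1.3 the rank test on raw change loses about 12 to 14 points against log change (49% against 63% at 1.0). At log-SD 0.5 every method has about 97% power or more for this effect.

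**A second set of assumptions.** Here the effect was rescaled so that the log-scale baseline-adjusted model has about 80% power, with log-SD 0.5 to 1.5 and correlation 0.5 or 0.7. The rank test trailed the t-test on logs by about 1 to 4 points for levels and by about 9 to 19 points for changes.

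**Model-based analyses.** The repeated measures ANOVA and the regression on fluid balance were not simulated. The nearest guide is the baseline-adjusted pair, raw against log: 78–79% against 92–93% at log-SD 0.8, 52–53% against 75–77% at 1.0, and 26–28% against 53–55% at 1.3. This shows that a raw-scale linear model loses power under skew; it does not measure the loss in the models the SAP plans.

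**Null.** At log-SD 1.0 and correlation 0.6, the rejection rate was 4.5% to 5.3% for every method.

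**The case against.** The strongest reply is that the plan already contains a robust option. The same table rows permit a non-parametric test and a non-parametric correlation. On levels, both are unchanged by a log transform, are not dominated by a few high values, and give the same p value if a ratio is inverted. Rank methods also treat values below an assay limit as ties, whereas logs need an extra rule. All of this stands, and it removes the point for levels and for correlations of levels.

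A second reply is that the comparison of about 53% with 75% sets two baseline-adjusted models against each other, and the SAP does not plan baseline adjustment for these markers. This also stands: the pair is only a guide to how a raw-scale model behaves.

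A third reply is that exact log-normality and a purely proportional effect favour logs, that the SAP gives neither skew nor effect size, and that these are exploratory outcomes of a pilot trial, to be reported in a separate manuscript. That limits the importance of the point but does not answer it for change scores. The SAP lists change as an analysis in its own right, and there the permitted rank test does not recover the loss.

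**Conclusion.** The point holds for three analyses: the raw change scores, even when ranked; the repeated measures ANOVA; and the exploratory regression on fluid balance. For change scores the loss is about 12 to 14 points of power with the rank test at log-SD 0.8 to 1.3, and about 32 points with the t-test at log-SD 1.0 (31% against 63%). These sizes rest on the assumed log-normal shape, correlation 0.5 and 30% reduction. For that effect the loss is negligible at log-SD 0.5. For the two model-based analyses the direction is clear, but the size was not computed.

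A reader might infer that a few high values dominate all the marker analyses and that most of their power is lost. The SAP does not support that, because it allows rank methods and on levels these come within a few points of a log analysis. Nor is there a false-positive problem. No primary, safety or clinical conclusion depends on this. It is a minor, cheap improvement.

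**What to change.** In the endothelial, inflammatory and renal rows of the outcome table:

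1. For right-skewed concentrations and ratios, replace the raw change from baseline with a linear model of the log follow-up value, with treatment group and the log baseline value as covariates. Report the geometric mean ratio with its 95% CI.
2. Use the log scale for the same markers in the repeated measures ANOVA and in the regression on fluid balance under Secondary analyses.
3. Keep the rank test and rank correlation as sensitivity analyses.
4. Name in advance the markers that stay on the raw scale because they are expected to be near symmetric, such as albumin and total protein.
5. State a substitution or censoring rule for values below the assay limit.

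Under the assumptions above at log-SD 1.0, item 1 raises power from about 49% (rank test on raw change) to 75–77%. About 14 points of that come from the log scale (49% to 63%); the rest comes from adjusting for baseline instead of subtracting it. The cost is SAP wording, with no new data. The one real burden is item 5.

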## Subgroup analyses

We will compare the primary outcomes and clinical outcomes between treatment groups in the following subgroups: patients with and without Acute Respiratory Distress Syndrome, Sepsis, Traumatic Brain Injury, and with hyper- and hypo-inflammatory phenotypes as previously defined [6].

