### Statistical analysis principles

The study will be analysed on an intention to treat basis. Multiple imputation will be used to deal with missing data. A p value of 0.05 will be considered as significant. A single final analysis is planned at the end of the trial.

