## Dummy Tables and Diagrams

The following are indicative of the approach used to present data, rather than the precise format.

Figure 1. Study flow diagram.

[figure not shown]

Table 1. Patient characteristics at randomisation.

Variables	Control	Intervention
Age	Mean (SD)	Mean (SD)
Gender:		
Male	N (%)	N (%)
Female	N (%)	N (%)
Type of admission:		
Emergency	N (%)	N (%)
Elective	N (%)	N (%)
Operative status:		
Surgical	N (%)	N (%)
Non-surgical	N (%)	N (%)
Primary organ system involvement:		
Respiratory	N (%)	N (%)
Cardiovascular	N (%)	N (%)
Neurological	N (%)	N (%)
Renal	N (%)	N (%)
Gastrointestinal	N (%)	N (%)
Other	N (%)	N (%)
Subgroups:		
Acute Respiratory Distress Syndrome	N (%)	N (%)
Sepsis	N (%)	N (%)
Traumatic Brain Injury	N (%)	N (%)
Hyperinflammatory phenotype	N (%)	N (%)
APACHE II score	Mean (SD)	Mean (SD)
Baseline SOFA score	Mean (SD)	Mean (SD)
KDIGO stage:		
1	N (%)	N (%)
2	N (%)	N (%)
3	N (%)	N (%)
Vasopressor use	N (%)	N (%)
Serum lactate	Mean (SD)	Mean (SD)
Renal Replacement Therapy use	N (%)	N (%)
Oxygenation index	Mean (SD)	Mean (SD)
Oedema in > 1 peripheral site	N (%)	N (%)
Cumulative fluid balance	Mean (SD)	Mean (SD)

Table 2. Key outcomes

	Control	Intervention	P value
Primary outcome			
Fluid balance over 24 hours up to Day 3 (mL)	Mean (SD)	Mean (SD)	x.xxx
Feasibility outcomes			
Cumulative fluid balance from ICU admission up to Day 3	Mean (SD)	Mean (SD)	x.xxx
Cumulative fluid balance from ICU admission up to Day 5	Mean (SD)	Mean (SD)	x.xxx
Clinical outcomes			
Mortality at 28 days:			
Total	N (%)	N (%)	x.xxx
Acute Respiratory Distress Syndrome	N (%)	N (%)	
Sepsis	N (%)	N (%)	
Traumatic Brain Injury	N (%)	N (%)	
Hyperinflammatory phenotype	N (%)	N (%)	
Duration of mechanical ventilation in survivors	Median (IQR) # , N=x	Median (IQR) # , N=x	x.xxx
Length of ICU stay in survivors	Median (IQR) # , N=x	Median (IQR) # , N=x	x.xxx
Change in SOFA scores baseline to day 3	Mean (SD)	Mean (SD)	x.xxx
Change in SOFA scores baseline to day 5	Mean (SD)	Mean (SD)	x.xxx
Incidence of new AKI (KDIGO Stage 3)	N (%)	N (%)	x.xxx
Before correction for fluid balance			
After correction for fluid balance			

\*Individual SOFA organ function scores to be reported in an appendix. #Mean (SD) to be reported if normally distributed

Table 3. Process measures

Recruitment rates (% of screened patients / % of admitted patients)*:			
Total	xx.x% / yy.y%		N/A

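### Subgroup plan compares arms inside each stratum, with no treatment-by-subgroup interaction and no exploratory label

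*SAP*

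**What the plan says.** The section on subgroup analyses is one sentence. It states "We will compare the primary outcomes and clinical outcomes between treatment groups in the following subgroups" and lists "patients with and without Acute Respiratory Distress Syndrome, Sepsis, Traumatic Brain Injury, and with hyper- and hypo-inflammatory phenotypes as previously defined". That is four factors with two levels each, so eight strata per outcome. No model is named.

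The only significance rule is in the section on statistical analysis principles: "A p value of 0.05 will be considered as significant". The section on secondary analyses adds a regression with treatment as the main exposure: "The following key covariates will be forced into the model: age, APACHE II score, presence of ARDS, vasopressor use at baseline". ARDS enters there as a main effect only.

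The dummy tables are introduced with "The following are indicative of the approach used to present data, rather than the precise format". Table 2 shows 28-day mortality by arm for ARDS, sepsis, traumatic brain injury and the hyperinflammatory phenotype, with empty p-value cells. It has no rows for the complementary strata, and no subgroup rows for the primary outcome or any other clinical outcome.

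**The concern.** A subgroup analysis should ask whether the treatment effect differs between, say, patients with and without ARDS. Comparing arms separately in each group answers a different question. One stratum can reach 0.05 and the other miss it only because they differ in size or by chance, although the true effect is the same in both. The ARDS covariate in the secondary regression is appropriate for adjusting the overall effect, but it assumes one common effect and does not fill this gap.

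This is a pilot, and its results may inform the population of a later trial. An apparent effect in one stratum and none in the other could steer that choice by chance.

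**Working it through.** **Reproducing the SAP's own figure.** The sample size section gives SD 1512 mL and a target difference of 750 mL, and states: "A sample size of 174 subjects (87 in each group) will have 90% power at a two-tailed significance level of 0.05". A two-sample t-test calculation with these inputs gives 86.4 per arm, rounded up to 87 (174 in total). Power at 87 per arm is 90.2%. The 3% drop-out allowance gives 174/0.97 = 179.4, so 180. The stated figures reproduce and are used below.

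**Assumptions.** The SAP gives no subgroup prevalences, so splits from 50/50 to 10/90 are assumed, with arms balanced inside each stratum and SD 1512 mL throughout.

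**Same effect in both strata (no true interaction).** With a and b patients per arm in the two strata, SE = 1512·√(2/a) and 1512·√(2/b). Stratum powers p1 and p2 come from the noncentral t distribution. P(exactly one significant) = p1(1−p2) + p2(1−p1). For 44 and 43 per arm at 750 mL: 0.633×0.377 + 0.623×0.367 = 0.467.

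| Per arm in strata | Power in each at 750 mL | Exactly one significant: 750 mL | 500 mL | 375 mL |
|---|---|---|---|---|
| 44 / 43 | 63.3% / 62.3% | 46.7% | 44.4% | 33.0% |
| 26 / 61 | 41.9% / 77.6% | 54.5% | 46.7% | 33.8% |
| 17 / 70 | 28.9% / 83.0% | 63.9% | 49.5% | 34.9% |
| 9 / 78 | 16.8% / 86.8% | 74.5% | 52.9% | 36.3% |

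At 250 mL the figure is 20.9-21.7%. With no effect it is 2×0.05×0.95 = 9.5%. An interaction test has a 5% false-positive rate in all these cases.

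**28-day mortality.** Exact binomial enumeration of the uncorrected chi-squared test, same splits, assumed event rates:

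| Mortality in the two arms | Exactly one stratum significant |
|---|---|
| 25% v 23% | 10.2-11.2% |
| 25% v 20% | 15.4-16.6% |
| 30% v 20% | 31.4-33.4% |

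**Multiplicity with no effect anywhere.** In a simulation of 10,000 trials with independent factors, assumed prevalences of 30/50/10/30% gave at least one of eight strata at p<0.05 in 25.6%, and at least one of four interactions in 18.7%. With all prevalences at 50%, the figures were 24.9% and 18.3%. For the four interactions, independence gives 1 − 0.95⁴ = 18.5%.

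**What an interaction test can deliver.** SE = 1512·√(2/a + 2/b) on 174 − 4 = 170 degrees of freedom. For 44/43 this is 458.5 mL, and the 95% CI half-width is 1.974×458.5 = 905 mL.

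| Split | Power, 750 mL in one stratum v 0 mL in the other | 95% CI half-width |
|---|---|---|
| 50/50 | 37.0% | 905 mL |
| 30/70 | 31.9% | 989 mL |
| 20/80 | 25.2% | 1141 mL |
| 10/90 | 16.8% | 1486 mL |

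**The case against.** The strongest reply is that the SAP may intend description only. Table 2 leaves the p-value cells empty for subgroup mortality. Table 3 does the same for the sub-rows of protocol violations, an outcome that the outcome table marks as descriptive, while the adverse event sub-rows do carry p-value placeholders. The subgroup sentence promises no stratum p-values and does not rule out an interaction model. This stands as a hint, but it covers one outcome in tables that the SAP calls indicative. Where the SAP means descriptive or exploratory, it says so, and it does not say so for subgroups. For the primary and other clinical outcomes, only the tests assigned in the outcome table and the 0.05 rule are available to the reader.

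A second reply is that 47-75% is the most striking case: a process measure at its full design effect. That is fair. For mortality with a small difference, the rate is close to the 9.5% expected with no effect.

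A third is that the remedy gains little, since interaction power is 17-37% and the chance of some false positive falls only from about 26% to 19%. That is also true. But low power is a reason to show the interaction estimate with its wide interval. It does not make within-stratum comparisons able to answer the question.

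Finally, nothing gives the subgroups confirmatory standing in a pilot with one primary endpoint. This limits the harm and makes the exploratory label easy to add.

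**Conclusion.** The concern holds. The only subgroup method stated cannot show whether effects differ, and the SAP contains no interaction test, interpretation rule or exploratory label for subgroups. If stratum results were judged at 0.05, a spurious contrast would appear within a pair in 47-75% of trials for the primary outcome at 750 mL, in 21-53% at 250-500 mL, and in 10-33% for mortality under the assumed rates. These figures rest on assumed splits and event rates, and on stratum p-values being read, which the SAP neither promises nor excludes. The primary analysis and the sample size are unaffected. The change should be made, but it concerns only how subgroup results are interpreted.

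**What to change.** Rewrite the subgroup section as follows.

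- For each of the four factors, fit one model with treatment, subgroup and their interaction: linear for fluid balance and SOFA change, logistic or Cox for binary or time-to-event outcomes.
- Report the interaction estimate with its 95% CI and p-value, and the treatment effect with 95% CI in both strata. Do not test significance within strata.
- Label the subgroup analyses exploratory, and state that four unadjusted interaction tests carry about a 19% chance of at least one false positive per outcome.
- State that a non-significant interaction is not evidence of a uniform effect.
- In Table 2, show both strata of each factor.

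The cost is SAP wording only, with no new data and no change in sample size. The drawback is imprecision: interaction power is about 17-37% for a 750 mL difference in effect, and every CI half-width (905-1486 mL) exceeds the 750 mL design difference. Multiplicity is reduced, not removed.
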